Appendix 9: Management Algorithms for Studies Under CTCAE Version 5.0

These general guidelines constitute guidance to the Investigator and may be supplemented by discussions with the Medical Monitor representing the Sponsor. The guidance applies to all immuno-oncology (IO) agents and regimens.

A general principle is that differential diagnoses should be diligently evaluated according to standard medical practice. Non-inflammatory etiologies should be considered and appropriately treated.

[figure not shown]
Corticosteroids are a primary therapy for IO drug-related AEs. The oral equivalent of the recommended IV doses may be considered for ambulatory subjects with low-grade toxicity. The lower bioavailability of oral corticosteroids should be taken into account when switching to the equivalent dose of oral corticosteroids.

Consultation with a medical or surgical specialist, especially prior to an invasive diagnostic or procedure, is recommended.

The frequency and severity of the related adverse events covered by these algorithms will depend on the IO agent or regimen being used.

GI Adverse Event Management Algorithm

Rule out non-inflammatory causes. If non-inflammatory cause is identified, treat accordingly and continue I-O therapy. Opiates/narcotics may mask symptoms of perforation. Infliximab should not be used in cases of perforation or sepsis.

[figure not shown]

Patients on IV steroids may be switched to an equivalent dose of oral corticosteroids (eg, prednisone) at start of tapering or earlier, after sustained clinical improvement is observed. Lower bioavailability of oral corticosteroids should be taken into account when switching to the equivalent dose of oral corticosteroids.

* Discontinue for Grade 4 diarrhea or colitis. For Grade 3 diarrhea or colitis, 1) Nivolumab monotherapy: Nivolumab can be delayed. 2) Nivolumab+ Ipilimumab combination: Ipilimumab should be discontinued while nivolumab can be delayed. Nivolumab monotherapy can be resumed when symptoms improve to Grade 1. Please refer to protocol for dose delay and discontinue criteria for other combinations.

Renal Adverse Event Management Algorithm

Rule out non-inflammatory causes. If non-inflammatory cause, treat accordingly and continue I-O therapy.

[figure not shown]

Patients on IV steroids may be switched to an equivalent dose of oral corticosteroids (eg, prednisone) at start of tapering or earlier, after sustained clinical improvement is observed. Lower bioavailability of oral corticosteroids should be taken into account when switching to the equivalent dose of oral corticosteroids.

Pulmonary Adverse Event Management Algorithm

Rule out non-inflammatory causes. If non-inflammatory cause, treat accordingly and continue I-O therapy.

[figure not shown]
Evaluate with imaging and pulmonary consultation.

Patients on IV steroids may be switched to an equivalent dose of oral corticosteroids (eg, prednisone) at start of tapering or earlier, after sustained clinical improvement is observed. Lower bioavailability of oral corticosteroids should be taken into account when switching to the equivalent dose of oral corticosteroids.

Hepatic Adverse Event Management Algorithm

Rule out non-inflammatory causes. If non-inflammatory cause, treat accordingly and continue I-O therapy.
Consider imaging for obstruction.

Patients on IV steroids may be switched to an equivalent dose of oral corticosteroids (e.g. prednisone) at start of tapering or earlier, after sustained clinical improvement is observed. Lower bioavailability of oral corticosteroids should be taken into account when switching to the equivalent dose of oral corticosteroids.

[figure not shown]
[^] Please refer to protocol dose delay and discontinue criteria for specific details.

*The recommended starting dose for AST or ALT > 20 x ULN or bilirubin >10 x ULN is 2 mg/kg/day methylprednisolone IV.

Endocrinopathy Adverse Event Management Algorithm

Rule out non-inflammatory causes. If non-inflammatory cause, treat accordingly and continue I-O therapy.

[figure not shown]
Consider visual field testing, endocrinology consultation, and imaging.

Patients on IV steroids may be switched to an equivalent dose of oral corticosteroids (eg, prednisone) at start of tapering or earlier, after sustained clinical improvement is observed. Lower bioavailability of oral corticosteroids should be taken into account when switching to the equivalent dose of oral corticosteroids.

Skin Adverse Event Management Algorithm

Rule out non-inflammatory causes. If non-inflammatory cause, treat accordingly and continue I-O therapy.

[figure not shown]
Patients on IV steroids may be switched to an equivalent dose of oral corticosteroids (e.g. prednisone) at start of tapering or earlier, after sustained clinical improvement is observed. Lower bioavailability of oral corticosteroids should be taken into account when switching to the equivalent dose of oral corticosteroids.

*Refer to NCI CTCAE v5 for term-specific grading criteria.

[^]If Steven-Johnson Syndrome (SJS), toxic epidermal necrosis (TEN), Drug Reaction with Eosinophilia and Systemic Symptoms (DRESS) is suspected, withhold I-O therapy and refer patient for specialized care for assessment and treatment. If SJS, TEN, or DRESS is diagnosed, permanently discontinue I-O therapy.

Neurological Adverse Event Management Algorithm

Rule out non-inflammatory causes. If non-inflammatory cause, treat accordingly and continue I-O therapy.

[figure not shown]

Patients on IV steroids may be switched to an equivalent dose of oral corticosteroids (eg. prednisone) at start of tapering or earlier, after sustained clinical improvement is observed. Lower bioavailability of oral corticosteroids should be taken into account when switching to the equivalent dose of oral corticosteroids.

[^]Discontinue for any grade myasthenia gravis, Guillain-Barre syndrome, treatment-related myelitis, or encephalitis.

Myocarditis Adverse Event Management Algorithm

Rule out non-inflammatory causes. If non-inflammatory cause, treat accordingly and continue I-O therapy.

Patients on IV steroids may be switched to an equivalent dose of oral corticosteroids (eg, prednisone) at start of tapering or earlier, after sustained clinical improvement is observed. Lower bioavailability of oral corticosteroids should be taken into account when switching to the equivalent dose of oral corticosteroids. Prophylactic antibiotics should be considered in the setting of ongoing immunosuppression.

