8.12.2. Dose Modifications and Management Associated with Nivolumab and/or Ipilimumab

Dose delay criteria apply for all drug-related adverse events (regardless of whether the event is attributed to nivolumab or ipilimumab or both). Delay administration of both nivolumab and ipilimumab if any of the delay criteria are met. Delay nivolumab and ipilimumab dosing for any adverse event, laboratory abnormality, or intercurrent illness which, in the judgment of the Investigator, warrants delaying the dose of study medication.

For subjects who require the delay of nivolumab and ipilimumab, re-evaluate weekly, or more frequently, if clinically indicated and resume dosing when criteria to resume treatment are met. Continue tumor assessments per protocol even if dosing is delayed.

If discontinuation criteria are met for ipilimumab but not for nivolumab, treatment with nivolumab may continue; if nivolumab is discontinued, however, ipilimumab will not continue as monotherapy.

If a subject meets criteria for discontinuation of nivolumab/ipilimumab and Investigator is unable to determine whether the event is related to both or one study drug, the participant must discontinue both nivolumab and ipilimumab. Subjects may continue receiving ivosidenib. If subject permanently discontinues treatment from all three drugs, EOT and Safety Follow-up Visits will be completed, as well as PFS follow-up (if disease has not progressed) and survival follow-up visits.

Subjects may resume treatment with nivolumab/ipilimumab if they have completed AE management (*i.e.* corticosteroid taper) or are on ≤ 10 mg prednisone or equivalent, and meet the requirements per [Appendix 8](#) and [Appendix 9](#).

Prior to re-initiating treatment in a participant with a dosing delay lasting > 8 weeks for Q3 week treatment and 10 weeks for Q4 week treatment, the Medical Monitor (or designee) must be consulted.

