8.12.3. Dose Modification for Ivosidenib, Nivolumab and Ipilimumab

When study interventions are administered in combination, attribution of an AE to a single component is likely to be difficult. When an AE cannot be clearly attributed to any one or combination of drugs, the most stringent criteria for dose modification (based on Dose modification for ivosidenib and ipilimumab/nivolumab - [Table \(8.12.1\) 1](#) and [Appendix 8](#)) must be used for all three drugs.

Dose delay: When study interventions are administered in combination, if the AE is considered immune-related, both nivolumab and ipilimumab interventions should be held according to recommended dose modifications ([Appendix 8](#)). QTc prolongation and other Grade3 or higher adverse events that are possibly related to ivosidenib should be managed according to dose modification recommendations in [Table \(8.12.1\) 1](#).

Re-starting Study Interventions: Subjects may not have any dose modifications (no change in dose or schedule) of nivolumab and/or ipilimumab in this study. At the 250 mg QD dose level, no dose re-escalation is allowed for ivosidenib. If the toxicity does not resolve or the criteria for resuming treatment are not met, the subject must be discontinued from all study interventions. If the toxicities do resolve and conditions are aligned with what is defined in [Appendix 8](#) and [Table \(8.12.1\) 1](#) ivosidenib, nivolumab and/or ipilimumab may be restarted at the discretion of the Investigator.

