Appendix 8: Adverse Event Criteria for Delay, Resume, and Discontinue of Nivolumab and Ipilimumab

Drug-Related Adverse Event (AE) per CTCAE V5	Severity	Action Taken	Clarifications, Exceptions, and Resume Criteria
Gastrointestinal			
Colitis or Diarrhea	Grade 2	Delay dose	Dosing may resume when AE resolves to baseline.
	Grade 3	Nivolumab monotherapy: Delay dose	Dosing may resume when AE resolves to baseline.
		When administered with ipilimumab: Permanently discontinue Ipilimumab	Nivolumab monotherapy may be resumed when AE resolves to baseline. If Grade 3 diarrhea or colitis recurs while on nivolumab monotherapy, permanently discontinue.
	Grade 4	Permanently discontinue	
Renal			
Serum Creatinine Increased	Grade 2 or 3	Delay dose	Dosing may resume when AE resolves to Grade \leq 1 or baseline value.
	Grade 4	Permanently discontinue	
Pulmonary			
Pneumonitis	Grade 2	Delay dose	Dosing may resume after pneumonitis has resolved to Grade \leq 1.
	Grade 3 or 4	Permanently discontinue	
Hepatic			
Aspartate aminotransferase (AST), alanine aminotransferase (ALT), or total bilirubin (T.bili) increased	AST or ALT $>$ 3 x and \leq 5 x upper limit of normal (ULN) or T.bili $>$ 1.5 x and \leq 3 x ULN, regardless of baseline value	Delay dose	Dosing may resume when laboratory values return to baseline.
	AST or ALT $>$ 5 x ULN or T.bili $>$ 3 x ULN, regardless of baseline value	Delay dose or permanently discontinue	In most cases of AST or ALT $>$ 5 x ULN, study treatment will be permanently discontinued. If the Investigator determines a possible favorable benefit/risk ratio that warrants continuation of study treatment, a discussion between the Investigator and the Medical Monitor/ designee must occur and approval from Medical Monitor prior to resuming therapy.
	Concurrent AST or ALT $>$ 3 x ULN and T.bili $>$ 2 x ULN, regardless of baseline value	Permanently discontinue	

Drug-Related Adverse Event (AE) per CTCAE V5	Severity	Action Taken	Clarifications, Exceptions, and Resume Criteria
Endocrinopathy			
Adrenal Insufficiency	Grade 2 adrenal insufficiency	Delay dose	Dosing may resume after adequately controlled with hormone replacement.

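### After Grade 3 diarrhea or colitis on nivolumab plus ipilimumab, the Appendix 9 GI footnote lets nivolumab restart at Grade 1, whereas the binding Appendix 8 criterion is resolution to baseline

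*Protocol*

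**What the plan says.** Appendix 8 tabulates the delay, resume and discontinue criteria for the two antibodies. In the colitis or diarrhea row, a Grade 3 event while ipilimumab is being given means permanent discontinuation of ipilimumab, and then "Nivolumab monotherapy may be resumed when AE resolves to baseline".

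Appendix 9 reproduces management algorithms and introduces them with "These general guidelines constitute guidance to the Investigator". The footnote to its GI algorithm takes up the same Grade 3 event on the same two-drug regimen: stop ipilimumab, delay nivolumab, and "Nivolumab monotherapy can be resumed when symptoms improve to Grade 1". It ends with "Please refer to protocol for dose delay and discontinue criteria for other combinations".

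Two sections of the protocol body govern restarting. Section 8.12.2 makes resumption of the antibodies conditional on the requirements of Appendix 8 and Appendix 9 together. Section 8.12.3 makes restart conditional on Appendix 8 and Table (8.12.1) 1, does not mention Appendix 9, and adds: "If the toxicity does not resolve or the criteria for resuming treatment are not met, the subject must be discontinued from all study interventions".

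**The concern.** Two appendices of one protocol give different restart thresholds for the same toxicity, and both are cited as requirements in 8.12.2. A participant with Grade 0 GI status at baseline whose Grade 3 event has improved to Grade 1 may restart under the footnote but not under Appendix 8.

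The restart threshold has consequences. Under Appendix 8, a further Grade 3 episode on nivolumab monotherapy means permanent discontinuation. What is at stake is dosing safety and consistency between sites. No sample size, endpoint or analysis depends on it.

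**Working it through.** There is no plan figure to reproduce. The check compares the texts and then sizes the exposed window.

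**1. Same situation?** Yes. Both texts address Grade 3 diarrhea or colitis on nivolumab plus ipilimumab, and both stop ipilimumab and hold nivolumab. Only the restart threshold differs.

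| GI status at baseline | Status at restart decision | Appendix 8 | Appendix 9 footnote |
|---|---|---|---|
| Grade 0 | Grade 1 | no restart | restart permitted |
| Grade 0 | Grade 0 | restart permitted | restart permitted |
| Grade 1 | Grade 1 | restart permitted | restart permitted |

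**2. Is baseline loose wording in Appendix 8?** Probably not. Other Appendix 8 rows, such as creatinine, uveitis and other drug-related events, accept Grade 1 or lower as an alternative to baseline. The colitis and diarrhea row gives baseline alone, at both Grade 2 and Grade 3.

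**3. Which text binds?** If both appendices must be met (8.12.2), the stricter one decides. Section 8.12.3 ties restart to Appendix 8, and the Investigator discretion it grants applies only once those conditions are met. Both routes lead to baseline, but the reader has to infer this because neither section ranks the appendices. Section 8.7 does not help: for immune-related dose modification it cites Appendix 8 and Appendix 10, and Appendix 10 covers performance status and concomitant medication.

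**4. Does the footnote send the reader back?** Only for other combinations, and only for delay and discontinue criteria. The hepatic footnote in the same appendix has no limit to other combinations: "Please refer to protocol dose delay and discontinue criteria for specific details".

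**5. Exposed window.** Inputs: four ipilimumab doses, one per 21-day cycle (synopsis); DLT window of 42 days (4.1.4.2).
- Ipilimumab cycles: 4 × 21 = 84 days, if no dose is delayed.
- Outside the DLT window: 84 − 42 = 42 days (Cycles 3 and 4).

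Within the first 42 days, a DLT requires Sponsor approval before any of the three drugs resumes (4.1.4.3). Applying 4.1.4.2 to treatment-related events:

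| Grade 3 event in days 1–42 | DLT? | Days without the approval step |
|---|---|---|
| Colitis | yes | 42 |
| Diarrhea, not immune-related | yes (not among the listed exclusions) | 42 |
| Diarrhea, immune-related, not at Grade 2 within 7 days, or not at Grade 1 or baseline within 14 days | yes | 42 |
| Diarrhea, immune-related, meeting both time limits | no | 84 |

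The last row includes the case the footnote describes: prompt improvement to Grade 1.

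**6. Number concerned.** At most the 7 participants enrolled (SAP section 5). The documents give no Grade 3 GI event rate for the three-drug combination, so no expected count is calculated.

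**The case against.** The strongest reply is that the operative text already settles the matter. Appendix 9 is general guidance for immuno-oncology agents, 8.12.2 and 8.12.3 both lead to the Appendix 8 criterion, and the correction changes no rule. That stands as a reason for low severity. It does not remove the point, because the footnote states a permission the body text does not give, and 8.12.2 calls on Appendix 9 as a requirement without ranking it.

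It can also be argued that ivosidenib makes this regimen one of the other combinations for which the footnote refers to the protocol. That is possible, but the footnote names nivolumab plus ipilimumab expressly and its referral does not mention resume criteria. The GI algorithm figure is not shown, so whether it points to Appendix 8 cannot be checked.

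Three stronger readings are tempting and not supported:
- A reader might infer that the protocol authorizes restart at Grade 1. It does not, once 8.12.2 and 8.12.3 are applied.
- A reader might infer that a participant who stays at Grade 1 must lose all three drugs. Section 8.12.3 says so, but 8.12.2 lets subjects continue ivosidenib when both antibodies are discontinued, and 4.1.1.3 lets one IMP continue from Cycle 5 with Sponsor approval. The point is unsettled.
- A reader might infer that participants remain exposed after termination. Section 4.3.1 allows continued IMP only if the study stopped for reasons other than safety; a safety termination stops treatment. The SAP gives the letter date, 21 August 2024, but no reason.

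**Conclusion.** The inconsistency is real, and the footnote is the text to correct. Its size is one CTCAE grade in the nivolumab restart threshold. It affects a participant with Grade 0 GI status at baseline whose Grade 3 event arises while ipilimumab is being given and who still has Grade 1 symptoms. The window without a Sponsor-approval step is 42 days for most such events and 84 days for immune-related diarrhea that improves quickly.

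This assumes no dose delay and a site that acts on the footnote without consulting Appendix 8 or sections 8.12.2 and 8.12.3. With 7 participants enrolled, the study terminated and no affected participant shown, severity is minor. That Appendix 8 prevails is an inference from the body text, though a well-supported one.

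**What to change.** In the Appendix 9 GI footnote, replace the Grade 1 threshold with resolution of the event to baseline and add a cross-reference to Appendix 8. In 8.12.2, add one sentence saying that Appendix 8 governs where the two appendices differ. If no further amendment is planned, send a note with the same content to any site that still has a participant on treatment.

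The drafting cost is one line and one sentence, or one note. The clinical cost is a longer nivolumab delay, or permanent nivolumab discontinuation, for a participant who stays at Grade 1. Sections 8.12.2 and 8.12.3 already impose that cost, so the change adds no new restriction. The same edit could usefully say whether ivosidenib may continue in that case, since 8.12.2 and 8.12.3 point in different directions.

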Appendix 10: ECOG Performance Status and Prohibited Concomitant Medications

Table 1 Eastern Cooperative Oncology Group Performance Status Scoring

Grade	Symptomatology
0	Fully active, able to carry on all pre-disease performance without restriction
1	Restricted in physically strenuous activity but ambulatory and able to carry out work of a light or sedentary nature, e.g., light housework, office work
2	Ambulatory and capable of all self-care but unable to carry out any work activities. Up and about more than 50% of waking hours
3	Capable of only limited self-care, confined to bed or chair more than 50% of waking hours
4	Completely disabled. Cannot carry on any self-care. Totally confined to bed or chair
5	Dead

Table 2 Prohibited Concomitant Medications

Prohibited medications and certain foods are not allowed in this study while subjects are receiving study drug.	
Strong CYP3A Inducers	CYP3A Substrates with a Narrow Therapeutic Window
Avasimibe, carbamazepine, enzalutamide, mitotane, phenytoin, rifampin, rifabutin, St. John's wort	Alfentanil, astemizole ¹ , cyclosporine, dihydroergotamine, ergotamine, fentanyl, pimozide, quinidine, everolimus, sirolimus, tacrolimus, terfenadine ¹

Note that this is not an exhaustive list. For an updated list, see the following link <http://www.fda.gov/Drugs/DevelopmentApprovalProcess/DevelopmentResources/DrugInteractionsLabeling/ucm080499.htm>
 "CYP substrates with a narrow therapeutic window" refers to drugs whose exposure-response relationship indicates that small increases in their exposure levels by the concomitant use of CYP inhibitors may lead to serious safety concerns (e.g., Torsades de Pointes).

¹ Withdrawn from the United States market because of safety reasons.

Table 3 New York Heart Association Classification

Class	Symptomatology
I	No limitation of physical activity. Ordinary physical activity does not cause undue fatigue, palpitation, dyspnea, or anginal pain.
II	Slight limitation of physical activity. Comfortable at rest, but ordinary physical activity results in fatigue, palpitation, dyspnea, or anginal pain.
III	Marked limitation of physical activity. Comfortable at rest, but less than ordinary activity results in fatigue, palpitation, dyspnea, or anginal pain.
IV	Unable to carry on any physical activity without discomfort. Symptoms at rest. If any physical activity is undertaken, discomfort is increased.

Source The Criteria Committee of the New York Heart Association. Nomenclature and Criteria for Diagnosis of Diseases of the Heart and Great Vessels. 9th ed. Boston, Mass: Little, Brown & Co; 1994:253-256.

Fridericia's Formula

$$QTcF = QT/RR^{1/3}$$

Table 4 Medications Known to Prolong the QT Interval

amiodarone	dofetilide	grepafloxacin	moxifloxacin	quinidine
astemizole	dolasetron	halofantrine	norfloxacin	sevoflurane
azithromycin	domperidone	haloperidol	ofloxacin	sotalol
bepridil	droperidol	ibutilide	ondansetron	sparfloxacin
chloroquine	erythromycin	itraconazole	palonosetron	terfenadine
chlorpromazine	escitalopram	ketoconazole	pentamidine	thioridazine
ciprofloxacin	flecainide	levofloxacin	pimozide	voriconazole
citalopram	gatifloxacin	levomethadyl	posaconazole	
clarithromycin	gemifloxacin	mesoridazine	probucol	
disopyramide	gransetron	methadone	procainamide	

For a complete and updated (ongoing) list of medications, please use the following link <https://crediblemeds.org/healthcare-providers/>

Table 5 Examples of Strong and Moderate CYP3A4 Inhibitors

Moderate CYP3A4 Inhibitors
Aprepitant, cimetidine, ciprofloxacin, clotrimazole, crizotinib, cyclosporine, dronedarone, erythromycin, fluconazole, fluvoxamine, imatinib, tofisopam, verapamil
Strong CYP3A4 Inhibitors
Boceprevir, clarithromycin, conivaptan, grapefruit juice, indinavir, itraconazole
Ketoconazole, lopinavir/ritonavir, mibefradil, nefazodone, nelfinavir, posaconazole
Ritonavir, saquinavir, telaprevir, telithromycin, voriconazole

Note Based on FDA guidelines; Investigators should follow local institutional guidelines, where appropriate.

